2.2.3 Preliminary Data

The proposed study builds upon the successful Jefferson/CIP research collaboration and the work completed through a prior Merck MISP-funded project. That project was a single group observational cohort study

testing the effect of the Pharmacists' Pneumonia Prevention Program (PPPP) on participant's vaccination knowledge, beliefs, and activation. In addition, as described above, an economic analysis was conducted to measure PPPP's intervention costs and to identify opportunities for increasing its efficiency.

[figure not shown]
PPPP was delivered to **203 older adults at predominantly African American senior centers and other community based venues** in
Philadelphia eight times in 2014, and consisted of: 1) a pharmacist-delivered
30 minute formal presentation, 2) a 10 minute culturally-sensitive live skit
performed by senior center actors, 3) small group action planning facilitated
by pharmacists, and 4) optional pneumococcal vaccination. Participants'
pneumonia and vaccination knowledge, beliefs, and activation were
measured at baseline, post-test, and 3 months.

Findings indicated that **PPPP significantly improved knowledge** of pneumococcal disease and immunization in an older, minority population using a novel senior center model of care. Specifically, there was a 54% increase in the total mean knowledge score among participants from baseline to 3 months. These findings are important because understanding pneumococcal disease and vaccination importance have consistently been linked to receipt of the vaccine ²⁰⁻²⁶

In addition, an increase in activation was observed among PPPP participants. More than one-third of participants who had not received the vaccination or had an unknown vaccination status at the start of the program stated that they received the vaccination as a result of PPPP participation. Participants also reported taking other activation steps including speaking with physicians and pharmacists about pneumococcal disease and vaccination as well as engaging in conversations with family members and friends about the topic.

In addition to knowledge, beliefs about immunizations can influence a person's decision to receive a vaccine. At baseline in the PPPP study, 21% believed that the pneumococcal vaccine would prevent pneumonia. This proportion more than doubled following the program, PPPP participants' trust in pharmacists also significantly improved; the proportion of participants who trusted pharmacists as immunizers was only 16% at baseline but increased to nearly 50% immediately after the program. However, participants' trust in pharmacists was consistently lower than of physicians at the measurement time points. This indicates that sustained trust in pharmacists as immunization providers is not something that can be attained through a single brief program. Trust takes time to build. The proposed study will help to further this trust through additional outreach and education.

The economic analysis conducted as a part of the prior study revealed PPPP's costs to be \$119/per participant. Resources were driven by costs of planning time (36.2%), program delivery (26.3%), and vaccine related expenses (23.8%). Vaccine costs were large despite only 18 attendees who received the vaccine (\$7,861 total, including acquisition costs and storage). These costs were high due to the acquisition prices of the product itself as well

[figure not shown]
2.5.1 Overview

This study will test two different vaccine educational programs delivered to older adults in the Delaware Valley region. IRB approval and clinicaltrials.gov listing will be obtained prior to study initiation, and informed consent will be obtained in accordance with IRB requirements. The project will be conducted under the leadership of [name] of Rutgers University, who will serve as Principal Investigator.

The PHARM and PEER interventions will be designed using the conceptual framework employed for our prior PPPP study (Figure 2). This framework was developed by our team based on a March 2015 CIP member survey in combination with findings from our previous work on a pharmacist-delivered pneumococcal vaccination program with CIP and a review of the medical literature. The framework outlines barriers to vaccination in the target population, and indicates which of these barriers can be addressed through a senior center model of care as well as which can be addressed through educational interventions.²⁷⁻³⁰ The area of overlap indicates barriers which we believe can be addressed both by use of the senior center model of care and a pharmacist- and peer-led educational intervention.

2.5 Study Procedures

Inclusion criteria are 1) Age \geq 50; 2) can attend a 2-hour session (though both PHARM and PEER entail 60 minutes of intervention, an additional hour is needed to allow for informed consent and data collection); 3) speak and read English at \geq 4th grade level as determined by a brief reading passage; 4) cognitively intact as evidenced by an Abbreviated Mental Status Test score \geq 7.

The study will consist of two arms designed to educate participants about vaccine-preventable disease and vaccination: 1) PHARM will consist of a 60-minute didactic lecture delivered by a pharmacist and video clips pertaining to 3 vaccine-preventable diseases (zoster, pneumonia, and influenza), and 2) a peer-led intervention ("PEER") will consist of a 60 minute small-group session including roleplaying exercises on these three vaccine-preventable diseases. The components of these interventions will be designed to address specific barriers in our framework. The interventions will focus on pneumococcal disease and zoster but will include limited content on influenza because participants are likely to have questions about how the flu and its vaccination differ from pneumococcal diseases and zoster.

Because the primary goal of the program is participant education, vaccination will not be included as a component of the program. As noted, vaccine costs in our prior study were high, representing nearly a quarter of total program cost. In addition, only 10% of participants opted to get vaccinated through that program (though many reported receiving the pneumonia vaccination through other avenues, for example physician's office or community pharmacy). For the proposed study, both PHARM and PEER groups will receive a listing of local vaccination sites, including clinics and pharmacies within a 3 mile radius of the program location.

PEER will be delivered by 10 peer educators, each leading small groups of 5-6 participants, for a total of 158 PEER participants. **PHARM** will be

delivered to 3 groups of 50-55 participants, or possibly 6 groups of 25-30 participants for a total of 158 PHARM participants.

2.5.2 Detailed Description of Interventions and Procedures

Pharmacist-Led Educational Intervention ("PHARM")

In the **PHARM** intervention group, participants will be given a 60-minute formal presentation on vaccine-preventable diseases to address knowledge and beliefs related to zoster, pneumonia, and influenza and to address barriers to receiving vaccination. In several studies, it has been demonstrated that those who believe it is wise to receive vaccinations and those that have discussed vaccination with their healthcare provider are more likely to receive a vaccine.³¹⁻³³

The presentation will be delivered by a pharmacist ([name], TJU), be appropriate for participants' educational level, and aim to establish an understanding of the vaccine preventable illnesses. The presentation will specifically discuss the following: causes, symptoms and potential complications of infection, risk factors for developing the infection, the incidence and prevalence of disease, modes of transmission, and disease prevention through vaccination.

To improve the interactivity of the presentation, brief **30-60 second video clips excerpted from interviews with community members and physicians will be shown. Community member clips** will consist of older adults from the AA population who have experienced vaccine-preventable infections. These clips will provide culturally relevant testimony to the program audience and reinforce participant understanding of concepts introduced during didactic teaching. Previous studies have demonstrated that using patient testimonials can influence a person's healthcare decision making.^{34,35}

Peer-Led Small Group Intervention ("PEER")

Training of the PEER Educators: Peer educators will be recruited from an experienced cohort of peer educators at CIP. CIP is an experienced provider of peer facilitated heath education models. CIP staff has extensive experience recruiting and training peer educators. CIP has a core group of 8 volunteer peer leaders trained to facilitate CIP's current health promotion programs: the 6 week Stanford University model *Chronic Disease Self-Management Program*; the *Diabetes Self-Management Program*; and, *Ask Me 3* (a health literacy program where peers educate the community to ask three simple questions of their healthcare provider). Additionally, CIP's Living Well Players, a community health theater group comprised of older adults have used peer to peer approaches to develop and perform health education skits on a variety of topics including pneumonia (through our PPPP project).

A pharmacist ([name]) will train the peer educators about vaccinepreventable diseases over the course of two didactic sessions. Following this training, a third session will be held to train the peer educators on the script that they will deliver to participants. The script will include the key learning points to be taught by the peer educators to participants about vaccine preventable diseases and vaccination. The script will also include role-play exercises. In the role-play exercises, 3 vaccination-related scenarios (one for each disease- zoster, pneumonia, and influenza) will be delivered to illustrate situations participants might encounter when interacting with healthcare providers or friends/family. The skit and role-play exercises will be practiced as needed, under the leadership of CIP's project manager, to ensure that the peer educators are confident and consistent when delivering PEER.

After completing the training, peer educators' competency on PEER program content will be assessed through a formal multiple-choice knowledge test. Each peer educator must achieve a minimum score of 80% correct over all items assessed, and 100% correct for all items deemed "core" knowledge.

[figure not shown]
It is anticipated that 10 peer educators will be needed to deliver PEER. To ensure consistency in how the peer educators are trained, all 10 will be trained as a single cohort.

Delivery of the PEER Intervention: PEER will be run over a 60-minute session. On the day of the PEER program, participants will breakout into assigned small groups. During this session, peer educators will deliver the skit and complete the role play exercises. Participants will then be asked what key points they learned about vaccine-preventable diseases and vaccines. Finally, the peer educator will engage in a dialogue to clarify and summarize these key points.

Summary of PHARM and PEER Interventions and Procedures

A summary of the PHARM and PEER interventions and procedures is provided below.

Figure 3. Summary of Interventions and Procedures

Study data will be recorded using paper forms and input into IBM SPSS for analysis. Electronic data will be password-protected by CIP while enrollment and data collection are ongoing. Files will be checked to ensure deidentification prior to sharing with the Rutgers investigators who will complete the analyses.

2.7.2 Definitions of Study Measures

Study measures will be assessed at baseline, immediately following the program ("posttest"), and 1 month after the program. The baseline and posttests will be administered in person on the date of the intervention. The 1 month follow up will be administered by phone (with up to 4 attempts to reach the participant). It should be noted that the team considered a more distal follow up point (i.e., at 2 or 3 months), but based on experience with the prior PPPP study felt that an earlier follow up would make it easier to reach participants with fewer call attempts. If the reviewers of this proposal conclude that 1 month is too soon for a follow up, we are willing to revise our plan to include a follow up at 2 or 3 months.

Knowledge and awareness of vaccine-preventable disease (Objective 1):

Knowledge and awareness about the target vaccine-preventable diseases will be assessed with a 15-20 item inventory encompassing the following domains: susceptibility to infection, symptoms of disease, severity of illness, and vaccination with an emphasis on vaccine efficacy, safety, and eligibility. These items will be selected following a review of the literature since no single validated instrument exists to assess knowledge of all three target diseases. ^{28,29,32,33,36-40}

Similar to the prior pneumonia project, **pneumonia knowledge** will be assessed using an instrument developed by our group using previously published literature. The prior instrument consisted of 6 "check all that apply" questions. Each item correctly checked was worth 1 point, for a maximum possible score of 28 points (see Figure 4 for a summary). We plan to retain the same instrument for the proposed study in order to enable comparison of pneumonia knowledge between the studies. However, we will also add a module pertaining to **zoster knowledge** which takes the same form as the established instrument.

Figure 4. Summary of Pneumonia Knowledge Instrument

Knowledge Assessment Questions	Maximum Number of Correct Responses Possible
Who is at risk of getting pneumonia?	9
How can you catch pneumonia from an infected person who is near you?	4
Which of these are symptoms of pneumococcal disease?	5

I should call my doctor or get emergency help if I get any of the following problems after vaccination:	5
Which of the following are possible side effects of the pneumonia vaccine?	5
TOTAL SCORE	28

Beliefs about Vaccine-Preventable Diseases and Vaccination (Objective 2):

Belief measures will include participants' beliefs about the target diseases and vaccination and trust in healthcare providers and peers as information sources. Multiple studies evaluating vaccinations in older and minority populations have found that people who do not receive certain vaccinations are unaware of their risk of disease, do not believe they are susceptible to the disease, and are not aware of their eligibility to receive the vaccine or feel that the vaccine would not reliably prevent illness. ^{28,36-38} In contrast, literature indicates that those who reported receiving a vaccination understood their susceptibility to infection, were aware of their eligibility to receive a vaccination, received a recommendation from a healthcare provider and felt that vaccination was the best way to prevent disease. ^{28,40}

Our prior PPPP study demonstrated that a pharmacist-delivered educational program can increase participants' trust in pharmacists both as vaccinators and sources of information, but that such gains are short term (limited to the post-test). This finding suggests that pharmacist-delivered information does not lead to sustained trust in pharmacists. However, peers may be more readily accepted as an information source in this population, which may contribute to sustained trust. Thus the change in beliefs from baseline to post test and one month after the intervention will be assessed in both the PHARM and PEER groups to determine whether the PEER group experiences a greater level of sustained trust vs. the PHARM group.

Cost Analysis (Objective 3):

We propose to conduct a detailed cost analysis which examines PHARM and PEER intervention costs in terms of what each of these two programs cost per program participant. This will enable us to understand which approach, PHARM or PEER, is less costly to deliver. We hypothesize that PEER will be less costly then PHARM due to differences in staffing requirements. In fact, the main reason for inclusion of cost in the proposed study is to determine whether PHARM and PEER, each of which is less resource intensive then our prior pneumonia program, will be less costly but yield comparable efficacy.

Intervention costs for PHARM and PEER will be calculated as the monetary value of time and materials required to train involved personnel, and deliver PHARM and PEER as well as personnel travel costs. Data on personnel time requirements for delivering PHARM and PEER will be collected in real time by

trained staff members using time logs which document the time and staff members required for training and delivery of the program. These data will be monetized using the hourly wage rates plus fringe benefit costs of the involved personnel. Other costs include materials such as signage, a modest participant giveaway such as medication reminder cards and pill box, printing/duplication, and food/refreshments. All costs will be reported in \$US 2017, consistent with the intervention time period.

Activation (Objective 4):

Participant activation will be measured as percent of participants who report taking one or more actions towards receiving vaccination at one month post-intervention, such as discussion with a healthcare provider (physician/pharmacist) or friends/family and/or receiving vaccination for either pneumonia or zoster. For participants who report vaccination, we will report which (pneumonia, zoster, or both). Influenza vaccination activation will be excluded from this measure since influenza vaccination is widely promoted through other initiatives which could influence activation, such as onsite flu shots at CIP.

Satisfaction (Objective 5):

Satisfaction measures will include **participants' overall satisfaction** with the content and delivery of PEER vs PHARM, the extent to which the participant felt **engaged**, and their **satisfaction with information received**. Satisfaction will be measured only at post-test using a simple 5-10 item satisfaction survey adapted from our prior research.

2.7.3 Sample Size Justification

The sample size was calculated using G*Power 3.0.10 and is based on the primary outcome measure (difference between change in mean knowledge score from baseline to 1 month for PHARM vs PEER). We plan to use a two-tailed independent samples t-test with α =0.05 to determine the between-group difference in mean knowledge scores at each timepoint. We seek to examine the difference, if any, in the effectiveness of the two approaches, PHARM and PEER; specifically, we wish to determine if the two approaches have similar results to within 20% difference expecting large variability (50% standard deviation). This difference is detectable at a power of 0.8 with 121 participants in each arm of the study. To ensure an adequate sample size, we scaled up the sample size calculation using the attrition rate from the prior pneumonia project. Attrition rate in PPPP was $\frac{203-143}{203}$ =0.296 ≈30%; thus scaling up by 30% yields a total sample size of 316 (158 in each arm).

As a secondary outcome, consistent with the prior pneumonia project, we plan to use a two-tailed paired samples t-test to determine the within-group difference in mean knowledge score between timepoints. However, because within-group differences are easier to detect than between-group differences, the sample size is powered to detect the 20% between-group difference.

2.8 Specific Drug Supply Requirements	None – vaccination is not included as a component of this study.	
2.9 Adverse Experience Reporting	Not required since vaccination is not being offered through this study.	
2.10 Itemized Study Budget	Provided as attachment.	

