2.1.1 Hypotheses

- PHARM and PEER will achieve similar improvements in older adults' knowledge of vaccine preventable diseases (primary hypothesis)
- PHARM and PEER will improved beliefs about vaccinepreventable disease
- 3) **PEER will be a lower cost approach** to educating participants in the senior center compared to PHARM
- 4) PHARM and PEER will result in similar rates of participants taking one or more activation step(s) to obtain vaccination
- 5) Participants will be highly satisfied with the PHARM and PEER interventions

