TITLE: Randomized Trial of Peer-to-Peer Versus Pharmacist Education to

Improve Older Adults' Vaccination Knowledge Through the Senior Center Model of Care

CLINICALTRIALS.GOV

NCT NUMBER

NCT03239665

March 6, 2020 **DOCUMENT DATE:**

Overview of Statistical Analysis

The design of the study was a randomized trial with randomization to PHARM or PEER performed at the program date level. The primary outcome measure was a between-group comparison of change in knowledge for PHARM vs. PEER at BL vs. PT, and BL vs. M1. Secondary measures included between-group examinations of beliefs, trust, and activation at all 3 time points (BL vs. PT and M1). We also measured within-group differences in knowledge, beliefs, and activation and the intervention costs of PHARM and PEER, including program development, training and implementation.

Study data was recorded using paper forms and input into SAS Version 9.4 for analysis. Electronic data was password-protected by CIP while enrollment and data collection were ongoing. Files were checked to ensure de-identification prior to sharing with the Rutgers University investigators who completed the analyses.

Analysis was performed using an Intention-to-Treat (ITT) sample. This sample included all participants meeting study including criteria with ≥ 1 documented response from the baseline survey. In the case of missing data from the post-intervention or one-month follow-up survey, the matrix below was used to carry forward observations. For all tests, the significance level was chosen as $\alpha = 0.05$, and was downward adjusted via the Bonferroni method when appropriate.

Table 1. ITT approach for handling missing follow-up data.

BL Data	PT Data	M1 Data
Present	Present	Absent Utilize PT Data
Present	Absent	Present
	Utilize BL Data	
Present	Absent	Absent
	Utilize BL Data	Utilize BL Data

^{*}BL = baseline, PT = post-intervention, M1 = one-month follow-up

Baseline Demographics

Demographic analysis was carried out via t-test for continuous variables and Chi-square test for categorical variables.

Knowledge

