The number of correct responses to the knowledge items at each timepoint was calculated as a whole and by disease (pneumonia, influenza, zoster). Baseline knowledge was compared by race via Kruskal-Wallis test. Because the knowledge data were expected to be non-normal and integer-valued, knowledge items were assessed using nonparametric methods. Specifically, between-group differences in knowledge were assessed at each timepoint via Wilcoxon Rank-Sum test. Similarly, between-group knowledge differences across timepoints were assessed pairwise via Wilcoxon Rank-Sum tests with Bonferroni-corrected significance threshold of

 α =0.05/3=0.0167. Within-group differences in knowledge score across timepoints were tested pairwise using Wilcoxon Signed-Rank tests.

Beliefs

The percentage of respondents answering "Completely Agree" to each item at each timepoint was calculated and compared between PHARM and PEER, as in our PPPP study. Pairwise Wilcoxon Signed-Rank tests were run comparing within-group changes in beliefs across timepoints applying Bonferroni correction (α =0.05/3=0.0167). Either Chi-Square or Fisher's Exact tests were used to compare beliefs between groups at each timepoint, depending on expected cell counts.

Activation

For all participants, Chi-Square or Fisher's Exact testing was performed as appropriate at each timepoint to assess between-group differences in proportions of participants planning actions, including planning vaccination and planning to speak with a doctor, pharmacist, or family/friends, as well as actions taken, including vaccinations obtained and having spoken with a doctor, pharmacist, or family/friends.

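### The primary hypothesis is similar knowledge improvement, but every planned between-arm knowledge test has a null of no difference and no interval is read against the stated 20%

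*Protocol*

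**What the plan says.** Protocol 2.1.1 labels one hypothesis as primary: "PHARM and PEER will achieve similar improvements in older adults' knowledge of vaccine preventable diseases (primary hypothesis". Hypothesis 4 in the same list expects similar activation rates in the two arms.

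Protocol 2.7.3 takes the between-arm difference in knowledge change from baseline to 1 month as the primary outcome and plans a two-tailed independent-samples t-test at 0.05. It gives the 20% two roles. First it is a closeness limit: "we wish to determine if the two approaches have similar results to within 20% difference expecting large variability (50% standard deviation". Later in the section it is an effect to be found: "the sample size is powered to detect the 20% between-group difference". The section does not say what the 20% is a percentage of.

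The SAP (Overview of Statistical Analysis) describes the primary measure as a "between-group comparison of change in knowledge for PHARM vs. PEER at BL vs. PT, and BL vs. M1", where BL is baseline, PT the post-test and M1 one month. Its Knowledge section replaces the t-test with Wilcoxon rank-sum tests. For changes, "between-group knowledge differences across timepoints were assessed pairwise via Wilcoxon Rank-Sum tests with Bonferroni-corrected significance threshold of" 0.05/3 = 0.0167. The 20% does not appear in the SAP. Activation is compared by Chi-square or Fisher tests.

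**The concern.** A test whose null is no difference can produce evidence that the arms differ. If it does not reject, it has not shown that they are alike. Here alikeness is the labelled primary hypothesis, and neither document supplies the missing piece: an equivalence or non-inferiority test, an interval read against a limit, or a rule for interpreting a non-significant result.

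The Bonferroni step sharpens the problem. A threshold of 0.0167 protects against falsely claiming a difference. When the hoped-for answer is similarity, it makes that answer easier to reach by default.

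The choice of program is at stake. On cost, the protocol states: "We hypothesize that PEER will be less costly then PHARM due to differences in staffing requirements". If non-significance on knowledge were read as similarity, the cheaper program would be favored even where the data still allow a difference of 20% or more. Activation has the same gap, and there not even a limit is named.

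**Working it through.** **Inputs.** From Protocol 2.7.3: difference 20%, SD 50%, two-sided alpha 0.05, 121 per arm, 158 per arm after scaling, 30% attrition. From the SAP, Knowledge: alpha 0.0167 for changes. Assumptions: the 20% and the SD share one scale, observations are independent, the t-test approximates the rank-sum test, and carry-forward does not dilute the effect.

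**The plan's own figure.** The protocol states: "This difference is detectable at a power of 0.8 with 121 participants in each arm of the study". The scaling step reproduces: 121 × 1.30 = 157.3, rounded up to 158. The 121 does not: 20/50 = 0.40 SD, two-sided 0.05 and power 0.80 give 100 per arm for a t-test. That is a separate matter. Here 121 is taken as stated.

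**Step 1: how often a true 20% difference is non-significant.** SE = 50 × √(2/n). The rate comes from the noncentral t with 2n − 2 df and noncentrality 20/SE. The 111 is 158 × 0.70 = 110.6, rounded up.

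| n per arm | SE | alpha 0.05 | alpha 0.0167 |
|---|---|---|---|
| 111 | 6.71 | 15.7% | 28.6% |
| 121 | 6.43 | 12.7% | 24.2% |
| 158 | 5.63 | 5.7% | 12.6% |

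**Step 2: non-significance against an interval rule.** A result is non-significant when the observed difference is below t × SE. A 90% confidence interval (CI), which corresponds to two one-sided tests at 0.05, lies within ±20% only when the observed difference is below 20 − t × SE, with t at the 95th percentile.

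- 121 per arm, 0.0167: non-significant up to 2.411 × 6.43 = 15.5%. The 90% CI lies within ±20% only below 20 − 1.651 × 6.43 = 9.4%. Between 9.4% and 15.5% the test finds no difference while the interval still reaches 20%.
- 121 per arm, 0.05: 12.7% against 9.4%.
- 158 per arm, 0.0167: 13.5% against 10.7%.
- 158 per arm, 0.05: 11.1% against 10.7%, so the two rules nearly agree.

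**Step 3: randomization by program date.** The SAP describes "randomization to PHARM or PEER performed at the program date level". The design effect (DEFF) is 1 + (n/k − 1) × ICC, with k dates per arm. The intracluster correlation (ICC) is assumed to be 0.01 to 0.05. The range k = 3 to 6 is inferred from the 3 or 6 PHARM groups in Protocol 2.5; groups need not equal dates. With the planned test left unadjusted and a normal approximation, the rate is Φ((z × SE − 20)/(SE × √DEFF)), less a negligible lower tail.

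- 121 per arm, 0.05, k = 6, ICC 0.01: DEFF = 1 + 19.17 × 0.01 = 1.19. Φ((12.60 − 20)/7.02) = 14.6%.
- 121 per arm, 0.05, k = 3, ICC 0.05: DEFF = 1 + 39.33 × 0.05 = 2.97. Φ((12.60 − 20)/11.07), less a lower tail of about 0.2 points, is 25.0%.

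So 12.7% becomes about 15% to 25%. At 158 per arm and 0.0167, 12.6% becomes 15.0% to 26.9%.

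**Step 4: could similarity be shown if it were true?** At zero true difference and 158 per arm, without clustering, the chance that the 90% CI lies within ±20% is 2Φ(10.72/5.63) − 1 = 0.94. With clustering, t on 2(k − 1) df and averaging over the estimated variance, it is about 0.81 (k = 6, ICC 0.01; SE 6.30) down to 0.17 (k = 3, ICC 0.05; SE 10.65).

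**The case against.** The strongest reply is that intent is mixed. Objective 1 in Protocol 2.1 is to compare efficacy, 2.7.3 also says it looks for any difference between the approaches, and the SAP never restates the similarity hypothesis. The planned tests serve those statements well. This lowers the seriousness of the point. It does not remove the mismatch, because the one hypothesis marked primary is similarity.

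A second reply is that at 158 per arm and alpha 0.05 a non-significant result and an interval within ±20% nearly coincide. That is correct for independent observations. It does not carry over to the 0.0167 that the SAP applies to changes, nor to randomization by date.

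A reader might infer that the investigators intend to report a non-significant test as similarity. Neither document says so; they leave the reading open.

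A reader might also take the 20% as a share of the prior program's 54% knowledge gain while keeping the SD on the baseline score, which would make the limit much narrower and the rates far worse. Nothing supports mixing the bases in that way. The 20% and the 50% stand in one sentence and are naturally read on one scale. The 54% also belongs to a different program, measured at 3 months on pneumococcal knowledge.

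**Conclusion.** The point holds. Followed exactly, the plan can show that PHARM and PEER differ in knowledge change, but no planned analysis can support the primary hypothesis that they are similar.

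That conclusion follows from the tests themselves and needs no assumption about clustering. Its size does rest on the assumptions listed in the check. The range, 5.7% to 28.6% across the sample sizes and thresholds considered, is the rate at which a true difference as large as the plan's own 20% would go undetected, before any allowance for program date. The ICC is not in the documents and the number of dates is only inferred, so the clustered figures indicate direction and rough scale. The effect of carrying observations forward is not included.

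**What to change.** 1. Report the PEER minus PHARM difference in knowledge change with a CI that allows for randomization by program date. Do this for both primary contrasts in the SAP: baseline to 1 month, which is the protocol's primary, and baseline to post-test. State how the confidence level treats having two contrasts.
2. State what the 20% in Protocol 2.7.3 is a percentage of, and read the CI against it. The SAP is written in the past tense and the base was not fixed beforehand, so label this post hoc and descriptive. Say whether the CI excludes a 20% difference; otherwise call the result inconclusive.
3. Do not present a non-significant test as evidence of similarity, for knowledge or for activation. For activation, where no limit is given, report the risk difference with a CI.
4. Keep the rank-sum tests as planned.

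The cost is one added knowledge analysis, an interval for activation and some wording, with no new data or participants. Similarity becomes harder to claim. Even if the arms were truly equal, the chances in Step 4 show that the result could well be inconclusive once program date is allowed for.
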